### *Interventions*

Volunteers will be instructed to use the intervention, according to the prior randomization, once a day, every day, for 21 days. If the volunteer is health professional, it will be instructed to use the intervention twice a day, every day, for 21 days. Intervention specifications included:

- 1) APT™ T3X: The volunteers will be instructed to use 4 drops of tetracycline hydrochloride 3% (APT™ T3X) applied inside of the nasal channels and inside of nostrils.
- 2) Placebo: The volunteers will be instructed to use 4 drops of a formulation composed of FDA approved inactive ingredients applied inside of the nasal channels and inside of nostrils.

All volunteers will be instructed to record each intervention application and to send to a member of the research team in order to control and ensure the adherence to treatment.

### *Outcomes*

#### **Primary outcome**

The primary outcome measured will be the rate of contamination by COVID-19 measured through the rate of how many people will be infected with COVID-19 over the course of the study in each group. This outcome will be measured 22 days after the randomization i.e., after 21 days of application with APT™ T3X or placebo.

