# Methods

## *Trial design*

A two-arm, parallel randomized, triple-blinded (volunteers, care provider, and outcome assessor), placebo-controlled trial will be carried out. This trial it will be prospectively registered on clinicaltrials.gov.

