## *Volunteers and recruitment*

One hundred volunteers will be included in the trial (fifty volunteers per group). The inclusion criteria will be: over 18 years; good general health (without serious health problems); tested negative, by means of immunoglobulin (Ig) G and IgM serology tests and chain real-time polymerase chain reaction (RT-PCR), for COVID-19. The exclusion criteria will be: previous immunization against COVID-19; allergy to tetracycline hydrochloride; diagnosis of Lyme disease; immunocompromised; share housing with someone diagnosed with COVID-19 at the time of the baseline evaluation; serious illnesses, such as cancer, kidney failure, decompensated cardiorespiratory and metabolic diseases, etc.

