#### **Secondary outcomes**

The secondary outcomes will be presence of adverse events, number of adverse events and frequency of adverse events measured through self-report. In addition, other virus or bacteria contamination rate will be measured through the rate of how many people will be infected with influenza or pneumonia over the course of the study in each group. All secondary outcomes will be measured 22 days after the randomization i.e., after 21 days of application with APT™ T3X or placebo.

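### The primary outcome counts infections across the whole study, but only a Day 22 measurement is stated, with no test, specimen or case definition and no way to record earlier infections

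*Combined protocol and SAP*

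**What the plan says.** All references are to the combined protocol and SAP.

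- **Primary outcome** sets a cumulative count: "measured through the rate of how many people will be infected with COVID-19 over the course of the study in each group". On timing it adds: "This outcome will be measured 22 days after the randomization i.e., after 21 days of application with APT™ T3X or placebo". It gives no assay, specimen, positivity rule or case definition.
- **Volunteers and recruitment** is the only place where tests are named, as an entry condition: "tested negative, by means of immunoglobulin (Ig) G and IgM serology tests and chain real-time polymerase chain reaction (RT-PCR), for COVID-19". No specimen is given, and nothing says these tests are repeated. On vaccination it says: "The exclusion criteria will be: previous immunization against COVID-19". Vaccination after entry is not addressed.
- **Interventions** describes the only contact between randomisation and Day 22. Volunteers record each application, "to send to a member of the research team in order to control and ensure the adherence to treatment".
- **Secondary outcomes** uses self-report for adverse events: "number of adverse events and frequency of adverse events measured through self-report". Influenza and pneumonia are handled like the primary outcome: "other virus or bacteria contamination rate will be measured through the rate of how many people will be infected with influenza or pneumonia". They too have no test or case definition.
- **Trial design** describes the study as "triple-blinded (volunteers, care provider, and outcome assessor").
- **Statistical analysis** compares two proportions by chi-square or Fisher at the 5% level and says nothing about how cases are found.

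**The concern.** A count over 21 days of exposure needs either surveillance during those days or an end-of-study test that can look back over all of them. The plan commits to neither. The adherence log collects applications, not test results or illness. Self-report is tied to adverse events. The entry tests are not carried forward.

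Two things are at stake. First, infections that nobody records during follow-up may not be recoverable later, so this is a gap in data collection and not only in wording. Second, RT-PCR alone, serology alone and the two together count different people. With no written rule, a volunteer who is IgG positive and RT-PCR negative at Day 22 could be classified after the results are known.

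**Working it through.** **Plan's own figures.** The plan gives 50 per group and 100 in total, and 50 + 50 = 100. It states no control rate, effect size, power or dropout, so no figure of its own depends on ascertainment. What follows is illustration.

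**Assumptions (none is in the documents).** Infection time t is uniform on Days 0-21, so infection age at Day 22 is a = 22 − t, uniform on 1 to 22. RT-PCR turns positive L = 3 or 5 days after exposure and stays positive for W = 7, 10 or 14 days, with W = 21 as a long case. Antibodies appear S = 7, 10 or 14 days after exposure and persist.

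**Share of infections found at Day 22**

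1. RT-PCR alone: [min(22, L + W) − L]/21.
   - W = 7: 7/21 = 33.3%. W = 10: 10/21 = 47.6%. W = 14: 14/21 = 66.7%. These are the same for L = 3 and L = 5.
   - W = 21: (22 − 3)/21 = 90.5% or (22 − 5)/21 = 81.0%.
2. Serology alone: (22 − S)/21 = 15/21 = 71.4%, 12/21 = 57.1%, 8/21 = 38.1%.
3. Both: if RT-PCR positivity lasts until antibodies appear, (22 − L)/21 = 90.5% or 81.0%. Otherwise subtract the gap. With L = 3, W = 7, S = 14 the gap is 4 days: (19 − 4)/21 = 71.4%. Over the 18 combinations with W = 7 to 14 the range is 71.4%-90.5%, so 9.5%-28.6% are missed.

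**Effect on the comparison.** If both arms have the same capture share c, observed risks are c·p1 and c·p0. Their ratio is p1/p0, so c cancels. The difference shrinks to c(p0 − p1), and each arm's rate is understated.

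**Size of the precision loss.** Take an assumed control risk of 20% and active risk of 5%, 50 per arm, two-sided 5% (the plan writes two-tailed only for the t test). Power is exact, by enumeration.

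| Capture | Expected cases, control vs active | Fisher power |
|---|---|---|
| Full | 10.0 vs 2.5 | 50.8% |
| Both tests, 71.4%-90.5% | 7.1-9.0 vs 1.8-2.3 | 31.0%-44.4% |
| RT-PCR alone, 33.3%-66.7% | 3.3-6.7 vs 0.8-1.7 | 5.6%-27.6% |

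Uncorrected chi-square, which the plan also allows, gives 21%-44% for RT-PCR alone. With full capture it gives 66%, the same as a 30% control risk at 66.7% capture, since 30% × 0.667 = 20%. At control risks of 5% and 10%, with active risk again one quarter, Fisher power is only 2.1% and 15.9% even with full capture. That is a sample-size matter, separate from this point.

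**Why seroconversion is not simply added to the primary event**

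- *False positives.* Observed risk = pc + (1 − pc)(1 − specificity). At an assumed combined specificity of 98%, 20% vs 5% and c = 90.5%: control 0.181 + 0.819 × 0.02 = 0.197; active 0.045 + 0.955 × 0.02 = 0.064. The ratio moves from 0.25 to 0.33 (0.34 at c = 71.4%). At 95% specificity it is 0.42-0.45.
- *Infections acquired just before randomisation.* Someone infected up to L days earlier can pass both entry tests and seroconvert by Day 22. With the same daily risk before entry in both arms, the observed ratio is (0.25c + L/21)/(c + L/21). L = 3, c = 0.905: (0.226 + 0.143)/(0.905 + 0.143) = 0.35. L = 5, c = 0.714: (0.179 + 0.238)/(0.714 + 0.238) = 0.44.
- *Long RT-PCR window.* With W = 21, serology finds nobody extra. Setting RT-PCR specificity at 1 and combined specificity at 98%, counting either test lowers Fisher power by 0.6 to 6.0 points at control risks of 10%-30%.

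**The case against.** The strongest defence is that the outcome is already worded as cumulative, so Day 22 may be only the date on which the tally closes. The entry serology also gives a baseline against which seroconversion could be read. This stands in part. A reader might infer that the plan rests on a single RT-PCR and will lose a third to two thirds of infections. The documents do not say so, and the loss is a risk that depends on an unstated choice. But if Day 22 only closes the window, a method of collecting earlier infections is still needed, and none is described.

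A reader might also infer a biased treatment effect. The documents do not support that. Volunteers and the outcome assessor are blinded, so equal loss is the natural expectation, and equal loss leaves the risk ratio alone. If the specimen were nasal, product at the treated site could in principle affect detection, but no specimen is named and the documents give no figure for such an effect.

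A third tempting reading is that one missed case decides the trial. With Fisher and 50 per arm, 0 vs 6 gives p = 0.027 and 0 vs 5 gives p = 0.056. Uncorrected chi-square gives p = 0.022 for 0 vs 5, and its own boundary lies between 0 vs 3 (0.079) and 0 vs 4 (0.041). This fragility comes from the sample size and the threshold. A dropout or one chance infection would do the same, so it is not evidence about ascertainment.

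**Conclusion.** The point holds as a gap in outcome definition and data collection that should be fixed. What is certain from the text is that the outcome is cumulative, that Day 22 is the only stated measurement, that no test, specimen or case definition is attached to it, and that nothing records infections in between. The size is conditional. Under the assumed uniform infection times and detection windows, the share found runs from 33% to 90% according to the test chosen, and even both entry tests repeated at Day 22 would miss about 10%-29%. The consequence is fewer events, understated rates and lower precision. Where control risk is 20%-30% the loss of power could be material. At 5%-10% power is low whatever is captured. Influenza and pneumonia share the gap.

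**What to change.** 1. **Interventions:** add to the existing application log a question on any positive SARS-CoV-2 test (with its date) and any influenza or pneumonia diagnosis. Ask it again at Day 22.
2. **Primary outcome:** count as an event any documented positive SARS-CoV-2 test from randomisation to Day 22, or a positive RT-PCR at Day 22 with the specimen named. Settle this rule before unblinding.
3. **Seroconversion:** if the baseline IgG/IgM assays are repeated at Day 22, report seroconversion by arm as a separate sensitivity analysis. Record vaccination during the study and leave those volunteers out of it.
4. **Secondary outcomes:** apply the same capture to influenza and pneumonia.
5. **Alternative:** if a single Day 22 test is kept with no interim capture, restate the outcome as the prevalence of a positive test at Day 22.

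The comparison in Statistical analysis is unchanged.

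**Cost:** protocol wording, one or two log questions, and up to 100 RT-PCR tests at Day 22 if not already planned (plus up to 100 serology tests if item 3 is taken up). **Limits:** reported positives come only from volunteers who seek a test, some infections will still be missed, and a positive in the first days may reflect exposure before randomisation, which is why the date is worth recording.

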#### **Secondary outcomes**

The secondary outcomes will be presence of adverse events, number of adverse events and frequency of adverse events measured through self-report. In addition, other virus or bacteria contamination rate will be measured through the rate of how many people will be infected with influenza or pneumonia over the course of the study in each group. All secondary outcomes will be measured 22 days after the randomization i.e., after 21 days of application with APT™ T3X or placebo.

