The topical formulation APT™ Tetracycline 3% formulation (APT™ T3X), is a FDA registered, non-prescription product. This formulation is used in an off-label manner as an intranasal application for prevention of COVID-19 and other viruses. The APT™ T3X as a topical application will penetrate through and into the mucus layer and deeper. This barrier of coverage will provide a mitigation effect to decrease the viral load of exposure and infection. The efficacy of APT™ T3X is due to disrupting the lipid envelope in seconds, hence neutralizing the virus. Previous tests were performed with APT™ T3X and the results found were promising. However, these tests were performed only *in vitro* and clinical studies demonstrating the ability of the APT™ T3X to decrease viral exposure and contamination by COVID-19 are necessary to confirm the possible prophylactic effect, allowing the formulation to be widely distributed to the general population.

Therefore, the aim of this project will be to evaluate the efficacy of the APT™ T3X compared to placebo to decrease COVID-19 contamination rate in humans.

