### *Statistical analysis*

The results obtained will first be tested for normality using the Kolmogorov-Smirnov test. The chi-square test or Fisher's exact test for two independent proportions will be used in the statistical analysis of the primary outcome of this study, the COVID-19 contamination rate and for the secondary outcomes: presence of adverse events and another virus or bacteria contamination rate. For the other secondary outcomes, the number of adverse events and frequency of adverse events, the Wilcoxon test will be used if this outcome does not present a normal distribution. If this outcome presents a normal distribution, the two-tailed, unpaired t test will be used. The level of significance used will be 5% ( $p < 0.05$ ).

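### The three adverse-event outcomes treat mild and severe events alike, and no supplied section records severity, seriousness, medical care needed or stopping because of an event

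*Combined protocol and SAP*

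**What the plan says.** The Secondary outcomes section defines safety in one sentence: "The secondary outcomes will be presence of adverse events, number of adverse events and frequency of adverse events measured through self-report". On timing it adds: "All secondary outcomes will be measured 22 days after the randomization".

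The Statistical analysis section handles the presence of adverse events as a proportion: "The chi-square test or Fisher's exact test for two independent proportions will be used". For the other two it reads "the number of adverse events and frequency of adverse events, the Wilcoxon test will be used if this outcome does not present a normal distribution"; when the distribution is normal, "the two-tailed, unpaired t test will be used". The significance level is 5%.

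No supplied section defines an adverse event or 'frequency', or provides for a severity grade, seriousness, medical care needed, or stopping because of an event. The Interventions section has volunteers log their applications and send the log to the team, but its stated purpose is adherence.

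Two facts in Background and aim set the context. The formulation is a non-prescription topical product registered with the FDA, and its use in the nose is off-label. Of the earlier work with the formulation the section says "these tests were performed only" in vitro, and it looks ahead to wide distribution to the public if the effect is confirmed.

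**The concern.** The drops are a preventive product. They go to volunteers in good general health, daily for 21 days (twice daily for health professionals), by an off-label route. Whether wide use is acceptable depends heavily on how bad the adverse events are and whether people stop because of them. Under the three planned outcomes, a moment of stinging and a reaction needing medical care contribute equally. An imbalance in severe events could therefore sit unseen inside similar overall totals. These details are also hard to recover reliably once the trial is over, so the omission cannot be repaired at the analysis stage.

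**Working it through.** The plan states no adverse-event rate, power or effect size, so there is no planned figure to reproduce. The inputs from the documents are 50 volunteers per arm (Volunteers and recruitment), and the tests and 5% level (Statistical analysis). Two-sided tests are assumed throughout, because the plan states this only for the t test. All event rates below are assumptions.

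**1. What each outcome can distinguish**

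| Outcome | What it is | Does severity enter? |
|---|---|---|
| Presence | yes/no per volunteer, compared as proportions | no |
| Number | events per volunteer, Wilcoxon or t test | no |
| Frequency | undefined, Wilcoxon or t test | nothing says so |

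The application log can show that drops were stopped, but nothing asks why.

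**2. Equal totals.** Suppose 15/50 in each arm report any event. Fisher's test on presence gives p = 1.00. If 4 of the 15 active-arm cases were severe and none of the placebo cases were, p would still be 1.00. The split of 4/50 (8%) against 0/50 would appear only if severity had been recorded.

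**3. How often the planned tests would react.** Let m be the mild-event rate in both arms and s the severe rate in the active arm only, occurring independently. The active-arm rate of any event is 1 − (1 − m)(1 − s); for m = 30% and s = 4% this is 1 − 0.70 × 0.96 = 32.8%. Exact enumeration of Fisher's test on presence rejects in:

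| m | s = 4% | s = 10% |
|---|---|---|
| 10% | 4.0% | 16.0% |
| 20% | 4.1% | 10.9% |
| 30% | 3.8% | 7.8% |
| 50% | 3.9% | 5.8% |

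For the Wilcoxon test on number of events, 4,000 simulated trials were run per setting, with Poisson mild counts and at most one severe event per volunteer. With a mean of 0.3 mild events it rejects in 5.8% (s = 4%) and 13.2% (s = 10%). With a mean of 1.0 it rejects in 5.1% and 7.5%. At s = 4% both tests behave much as if there were no difference.

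**4. What recording severity would add**

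- The probability of seeing at least one severe case among 50 is 1 − (1 − s)^50. This is 64%, 87%, 96% and 99.5% for s = 2%, 4%, 6% and 10%.
- If none is seen, the exact upper 95% limit is 1 − 0.05^(1/50) = 5.8% one-sided, or 1 − 0.025^(1/50) = 7.1% two-sided.
- For k against 0, the two-sided Fisher p is 2 × C(50,k)/C(100,k):
  - 4 against 0: 2 × 230,300/3,921,225 = 0.117
  - 5 against 0: 2 × 2,118,760/75,287,520 = 0.056
  - 6 against 0: 2 × 15,890,700/1,192,052,400 = 0.027
- With no severe events on placebo, the power of that test is 0%, 1.4%, 7.8% and 38% for s = 2%, 4%, 6% and 10%.

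The gain is therefore descriptive and does not come from a test.

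**The case against.** The strongest reply is that a short outcome list does not stop staff from describing individual events, and that the application log already shows who stopped and when. Both points are fair. What remains is that neither severity nor the reason for stopping is specified for collection, so any description would depend on what volunteers happened to volunteer. Nor does the plan give a rule for concluding safety, so it cannot be said that equal totals would be declared equal safety, only that they could hide a difference.

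Four stronger readings are tempting, and the documents do not support them.

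- A reader might infer that the product has never been used in people. Background and aim limits only the previous tests to in vitro work and calls the formulation a registered non-prescription topical product, so earlier human use is not excluded.
- A reader might infer that number and frequency duplicate each other. That holds only if frequency means events divided by a fixed period. It could also mean days with an event, recurrences, or events per application, and that last denominator differs between once-daily and twice-daily users. The supportable criticism is that the term is undefined.
- A reader might take a split of 6 against 0 as typical of what would be missed. It is the smallest split against zero that reaches p < 0.05 at this size, and it is 12% of the arm, a rate no document figure supports.
- A reader might infer that testing a combined outcome of severe, medically treated or treatment-stopping events would solve the problem. It would again count a mild event that led to stopping the same as a severe reaction, and a test on severe events alone already has little power.

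**Conclusion.** The point holds as a gap in what is collected and reported. Followed as written, the trial could not state by arm how many volunteers had a severe or serious event, needed medical care, or stopped because of an event.

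On size: under the assumed rates, a 4% excess of severe reactions leaves the planned tests rejecting at about their nominal level, and a 10% excess is picked up in roughly 6% to 16% of trials. The zero-event limits assume that all 50 volunteers in the arm report. Pages removed from the public copy could not be checked, so the conclusion rests on the supplied sections.

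This is a cheap improvement, best made before enrolment. It does not show that the product is unsafe, and it does not invalidate the three planned outcomes.

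**What to change.** In Secondary outcomes, for each self-reported event also record:

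- severity (mild, moderate or severe);
- whether it was serious or needed medical care;
- whether the drops were stopped because of it.

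In Statistical analysis, state that the number and percentage of volunteers with at least one of each will be reported by arm, separately and descriptively, with exact 95% confidence limits, including when the count is zero. Say whether those limits are one-sided or two-sided. Label any between-arm test of these items exploratory. Keep the three existing outcomes and state what 'frequency' means, including its denominator.

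The cost is a few more items per reported event. The self-report form is not among the supplied documents, so the exact burden cannot be judged, but nothing here calls for an extra visit. The downside is a slightly longer self-report.

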## Background and aim

The new coronavirus 2019 (COVID-19) was declared a pandemic by the World Health Organization (WHO) due to the alarming levels of spread, severity and inaction. COVID-19 is caused by the SARS-CoV-2 virus (severe acute respiratory syndrome of coronavirus 2). The main clinical characteristics observed in patients infected with COVID-19 are: fever, dry cough, fatigue or myalgia. Patients infected with COVID-19 can present from no symptoms to pneumonia and death. Dealing with COVID-19 must be done on different fronts, such as mitigation, treatment and prevention. Therefore, strategies and therapies that can help reduce the COVID-19 rate of contamination are still important alternatives at this time of the pandemic, especially when mutations of the virus have been observed worldwide.

The Advanced Penetration Technology™ (APT™) is intellectual property owned by Patient Focused Tele-Health, LLC, a Rockwall, Texas based company. The company's focus is improving over-the-counter (OTC) topical formulations, allowing consumers better therapeutic outcomes with non-prescription medications. The Advanced Penetration Technology™ (APT™) is a patent-pending, proprietary transdermal dual carrier formulation. This formulation provides improved dermal penetration and efficacy of topical API's. Additionally, the APT™ imparts both a mechanical and biochemical effect on the microbe/fungal cell walls providing a highly effective method of destruction of microbes. These unique properties impart the broad spectrum anti-viral capability to the APT™ Tetracycline 3% formulation, breaking barriers in pharmacology and virology.

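### Could COVID-19 pneumonia be counted twice, in the primary outcome and in the secondary outcome for other infections?

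*Combined protocol and SAP*

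**What the plan says.** Under Secondary outcomes, the plan states that "other virus or bacteria contamination rate will be measured through the rate of how many people will be infected with influenza or pneumonia". It names no organism, diagnostic test or attribution rule for pneumonia. Under Primary outcome, the trial counts "the rate of how many people will be infected with COVID-19 over the course of the study in each group".

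The two outcomes share volunteers and timing. For the primary, "This outcome will be measured 22 days after the randomization"; for the rest, "All secondary outcomes will be measured 22 days after the randomization".

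Background and aim notes that "Patients infected with COVID-19 can present from no symptoms to pneumonia and death", and describes the product's use as "intranasal application for prevention of COVID-19 and other viruses".

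Statistical analysis assigns a chi-square or Fisher's exact test to the primary outcome and to "presence of adverse events and another virus or bacteria contamination rate". It says nothing about a volunteer who might qualify for both infection outcomes.

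**The concern.** Pneumonia is a syndrome, not an organism, and the plan itself says COVID-19 can cause it. If every pneumonia counts, a volunteer with COVID-19 pneumonia is an event in both outcomes.

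That would matter because this is the only outcome that bears on infections other than COVID-19. Suppose the product prevents COVID-19 and does nothing else. Fewer COVID-19 pneumonias on active would then lower the rate of supposedly other infections in that arm, and a carry-over of the primary effect would read as broader protection. The bias would arise when the trial's main hypothesis is true. If the product does not affect COVID-19, the overlap adds noise but no direction.

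**Working it through.** **Reading the sections together.** The measure (influenza or pneumonia) is wider than the name (infections other than COVID-19). The name is the only limit on cause, and it appears twice: as *other* under Secondary outcomes and as *another* under Statistical analysis. A natural pairing is influenza for the virus and pneumonia for the bacteria. On that reading a pneumonia due to SARS-CoV-2 does not belong in the count.

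**Size if the name were ignored.** The documents state no event rates, so there is no figure of theirs to reproduce. From the plan: 50 per arm. Assumed:

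- COVID-19 rate *c*: 10% on placebo, 2% on active
- share of COVID-19 cases with pneumonia *s*: 5% to 20%
- background influenza or non-COVID pneumonia *b*: 1% to 2% in both arms, so the true risk ratio is 1

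*Expected overlap* = 50 × c × s.

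- s = 5%: 50 × 0.10 × 0.05 = 0.25 on placebo and 50 × 0.02 × 0.05 = 0.05 on active, total 0.30.
- s = 20%: 1.00 and 0.20, total 1.20.

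*Chance of no overlapping case in the trial* = (1 − c₁s)^50 × (1 − c₂s)^50, with c₁ for placebo and c₂ for active.

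- s = 5%: 0.995^50 × 0.999^50 = 0.74.
- s = 20%: 0.98^50 × 0.996^50 = 0.30.

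*Apparent risk ratio*, with arm probability 1 − (1 − b)(1 − cs). The last column repeats the calculation with COVID-19 at 5% on active, that is, halved and not cut by 80%:

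| s | b | Expected events, placebo vs active (10% vs 2%) | Risk ratio, 10% vs 2% | Risk ratio, 10% vs 5% |
|---|---|---|---|---|
| 5% | 1% | 0.75 vs 0.55 | 0.74 | 0.83 |
| 5% | 2% | 1.25 vs 1.05 | 0.84 | 0.90 |
| 20% | 1% | 1.49 vs 0.70 | 0.47 | 0.67 |
| 20% | 2% | 1.98 vs 1.20 | 0.60 | 0.75 |

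The ratios look large because they divide expected counts below 2. The difference between arms is 0.20 to 0.79 of an event under 10% vs 2%.

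*Chance of a falsely significant result* (exact binomial enumeration, 10% vs 2%, two-sided 5%). Fisher's test gives p = 0.056 for 5 vs 0 events and 0.027 for 6 vs 0. The four rows give 0.007%, 0.07%, 0.18% and 0.45%. The plan also allows chi-square. Uncorrected, it reaches p = 0.041 at 4 vs 0, and the four rows give 0.5% to 4.6%, against 0.2% to 1.3% with no COVID-19 pneumonia counted. At such sparse counts Fisher's test is the usual choice.

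*Extreme inputs* (COVID-19 20% vs 5%, s = 30%, b = 5%): 5.35 vs 3.21 events, risk ratio 0.60, Fisher 4.9%.

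**Would an exclusion rule be cleaner?** Suppose pneumonia in a COVID-19-positive volunteer is dropped unless another organism is on record. The documents provide for no such records. If every background event is a pneumonia without a documented organism, and occurs independently of COVID-19, each arm keeps b(1 − c). The ratio becomes (1 − 0.02)/(1 − 0.10) = 0.98/0.90 = 1.09 where the truth is 1. This is a bias in the opposite direction, smaller than the overlap it replaces.

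**The case for a change.** The strongest reply is that a label is not a counting rule. Faced with pneumonia in a COVID-19-positive volunteer at day 22, one assessor could count it because the measure says pneumonia, and another could leave it out because the name says *other*. Co-infection is not addressed either. Definitions are best fixed before results by arm are known, and a sentence costs little. In so sparse an outcome a single reclassified event can move the ratio noticeably: in the four rows above, COVID-19 pneumonia would make up roughly 20% to 67% of placebo events, from cs/(b + cs).

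Part of this stands. The attribution rule is unwritten, and a sponsor who chose to write it down would do no harm by stating that pneumonia attributed to COVID-19 is not an *other* infection. But the two readings are not equally open, because only one agrees with the outcome's name in both sections. The large shares and ratios also need the less natural reading, a strong COVID-19 effect, and a 20% pneumonia share that the documents do not support. The plan enrols adults in good general health, excludes the immunocompromised and seriously ill, and follows them for about three weeks. It tests proportions and does not plan to report a risk ratio for this outcome.

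**Conclusion.** The plan needs no change on this point. It leaves a classification step unwritten, but the outcome's own name shows how to fill it: a pneumonia due to COVID-19 is not an *other* infection. The primary outcome and the sample size are unaffected on any reading.

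If the name were ignored altogether, the expected overlap would be 0.3 to 1.2 volunteers in the whole trial, and a false positive by Fisher's test would have a chance below 0.5%. Uncorrected chi-square would raise that to at most 4.6%, and only extreme inputs bring Fisher's test to a similar level. These sizes rest on assumed rates throughout, including an 80% reduction in COVID-19; a 50% reduction brings the apparent risk ratios nearer to 1, and no reduction removes the directional bias. A formal exclusion rule would tie the outcome to a post-randomisation event and to organism records the plan does not collect, so it offers little gain over sensible classification.
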